6.3.2.2.2. Categorical Variable

Each of the categorical secondary endpoints will be analyzed using a binary logistic regression model, incorporating the same covariates as the primary endpoint. The estimated odds ratio, 95% CI, and p-value will be presented. Patients who are unable to maintain asthma control or who withdraw treatment prematurely will be counted as nonresponders and analyzed as part of the lowest category of response. A frequency distribution bar graph will be provided for the number of patients in each of the categories by treatment group.

The following sample SAS[®] code pertains to the secondary efficacy analysis of categorical dose reduction; 'treatment' is the randomized group ('0'=placebo) and 'out_cat2' is the 2-level response category (1=worst category, 2=best category):

```
proc logistic data=<<>>;
  class treatment (param=ref ref='0') strata1 strata2;
  model out_cat2 (desc) = treatment strata1 strata2 ocsbase ocsdur / expb;
  contrast "odds ratio" treatment 1 -1 / estimate;
  ods output contrastestimate=<<>>;
run;
```

6.3.2.2.3. Other Sensitivity Analyses

Change from baseline to weeks 20 to 24 will additionally be analyzed using a non-parametric (Wilcoxon rank-sum) test in which the patient's rank is analyzed rather than the actual observed percent reduction. For patients who withdraw early or do not maintain asthma control between weeks 20 to 24, a rank corresponding to a value less than the smallest observed reduction among all patients will be imputed. The median and 95% CI will be calculated with the use of the Hodges-Lehmann estimate. The p-value will be based on the Wilcoxon rank-sum test.

To further assess corticosteroid burden, the total number of days corticosteroids are taken for exacerbations (defined in Section 6.3.3.1) and the total cumulative dose of corticosteroids taken during the entire study will be summarized separately by treatment group. Corticosteroids taken for exacerbations will be based on medication use, as per the CAE CRF. Cumulative dose will be the sum of the corticosteroid doses (prescribed for either asthma or CAE, as per the medication CRF) multiplied by the duration of corticosteroid treatment, taking dose frequency into account.

- If 5mg is prescribed once daily for 10 days, the cumulative dose is $5*10 = 50$.
- If 5mg is prescribed once every other day for 10 days, the cumulative dose is $5*5=25$.

The analyses of corticosteroid burden will include all oral, iv, and im corticosteroid preparations. Non-prednisone treatments will be converted to a prednisone equivalent dose using the conversion factors in Table 9. The list of medications will be reviewed and updated, if necessary, prior to unblinding. The final table will be documented in the minutes from the final Statistical Data Review meeting.

Table 9: Conversion of Corticosteroid to Prednisone-Equivalent Doses

Medication Type	Medication	Conversion Factor
Short-acting:	Cortisone	0.2
	Hydrocortisone	0.25
Intermediate-acting:	Methylprednisolone	1.25
	Meprednisone	1.25
	Prednisolone	1
	Prednisone	1
	Triamcinolone	1.25
Long-acting:	Betamethasone	8.33
	Dexamethasone	6.67

Analysis of the total cumulative dose of corticosteroids will be performed using an ANCOVA model with fixed effects for treatment, age group, OCS dose group, and baseline OCS dose as a covariate. Similarly, analysis of the total number of days corticosteroids taken for exacerbations will be performed using an ANOVA model with fixed effects for treatment, age group, and OCS dose group.

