2.4. Randomization and Blinding

This is a randomized, double-blind, placebo-controlled study. In order to achieve balance between treatment groups with regard to average daily OCS use/requirement and age, randomization will be stratified by optimized, average daily OCS dose (>10 mg or ≤10 mg) and age at baseline (12 to <18 years or ≥18 years). Within each stratum, patients will be randomly assigned to receive treatment with sc reslizumab at a dosage of 110 mg every 4 weeks or a matching placebo in a 1:1 ratio. This system is used to ensure a balance across treatment groups.

The randomization list and treatment will be assigned to the relevant treatment groups through a qualified contract research organization (CRO), eg, via Interactive Web Response System (IWRS). Generation of the medication list and management of the interactive response technology (IRT) system will be done by a qualified CRO under the oversight of Teva's Clinical Supply Chain.

The sponsor's personnel involved in the study will be blinded to the study drug identity after the run-in period until the database is locked for analysis and the treatment assignment is revealed, with the exception of the bioanalytical group (Global Bioassays and Technology), who will not be blinded in order to facilitate PK and ADA sample analysis. Eosinophils and monocytes will

be redacted from the post-baseline differential cell count reports to avoid the possibility of removing the blind.

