6.2.2. Primary Analysis

The primary endpoint is the 5-level categorical percent reduction in OCS dose during weeks 20 to 24, compared to the optimized dose at baseline. The primary analysis will incorporate data from all randomized patients. Patients who are unable to maintain asthma control or who

withdraw treatment prematurely will be analyzed as part of the lowest category of response. The primary endpoint will be analyzed using a proportional odds model including factors for treatment group and the randomization strata (age and OCS dose, as defined in Section 2.4); baseline OCS dose and duration of OCS use prior to study entry will also be included as covariates. Age and OCS dose will be based on data recorded in the clinical database.

The proportional odds ratio (reslizumab/placebo) will be estimated from this model, representing the ratio of the odds of a patient outcome being in a higher OCS dose reduction category for reslizumab compared to placebo. The estimated odds ratio, 95% CI, and p-value will be reported. A frequency distribution bar graph will be provided for the number of patients in each of the 5 categories by treatment group.

The following sample Statistical Analysis Software (SAS[®]) code pertains to the primary efficacy analysis of categorical dose reduction; ‘treatment’ is the randomized group (‘0’=placebo) and ‘out_cat5’ is the 5-level response category (1=worst category, ..., 5=best category):

```
proc genmod data=<<>> order=internal descending;
  class treatment (param=ref ref='0') strata1 strata2;
  model out_cat5 = treatment strata1 strata2 ocsbase ocsdur
    / dist=mult link=cumlogit aggregate=treatment type3;
  estimate "odds ratio" treatment 1 -1 / exp;
  ods output parameterestimates=<<>>;
run;
```

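### The Wilcoxon check on OCS reduction gives failures only a worst rank, but reports a Hodges-Lehmann estimate and interval that depend on an unstated number for them

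*SAP*

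**What the plan says.** SAP 6.3.2.2.3 adds a check on the continuous OCS change to weeks 20–24, which "will additionally be analyzed using a non-parametric (Wilcoxon rank-sum) test in which the patient's rank is analyzed rather than the actual observed percent reduction". The rule for failures, meaning early withdrawal or loss of asthma control, is that "a rank corresponding to a value less than the smallest observed reduction among all patients will be imputed". Two outputs follow: "The median and 95% CI will be calculated with the use of the Hodges-Lehmann estimate", and "The p-value will be based on the Wilcoxon rank-sum test".

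The section leaves three things open:

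- It gives no number for the failures.
- It does not say whether the Hodges-Lehmann median is a between-group shift (the natural reading) or something else.
- It names no strata for the test.

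Elsewhere the strata are used. SAP 2.4 says "randomization will be stratified by optimized, average daily OCS dose", and also by age. The primary analysis in SAP 6.2.2 is "a proportional odds model including factors for treatment group and the randomization strata". The MMRM in SAP 6.3.2.2.1 and the corticosteroid-burden models in 6.3.2.2.3 itself also carry both factors.

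SAP 6.2.1 and 6.3.2.1.1 define reduction as the later dose minus the baseline dose, so a fall in dose is a negative number.

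**The concern.** A rank test needs only order, so a tied worst rank fully defines the Wilcoxon p-value. The Hodges-Lehmann estimate is the median of all numeric differences between a reslizumab patient and a placebo patient, and its interval uses order statistics of the same differences. A patient who has only a rank cannot enter that calculation until someone picks a number. Any number below the observed minimum satisfies the text, so two programmers could both follow the SAP and report different effects.

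This matters because percent change in OCS dose is the third secondary endpoint (SAP 6.3.1). Its MMRM uses observed data only (SAP 4.4). The Wilcoxon analysis is the planned check on the continuous change that counts withdrawal and loss of control as failure, so a percentage-point effect from it may well be quoted.

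Two smaller points sit in the same paragraph. The test omits the randomization factors. And under the SAP's own sign convention, a value less than the smallest reduction would, taken literally, lie at the favourable end.

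**Working it through.** **Inputs from SAP 2.3.** Placebo shares, worst to best category: 55.6, 10.8, 14.8, 7.9, 10.9%. Odds ratio 2.63, alpha 0.05 (two-sided, SAP 4.3), 76 per group, 90% power.

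**Reslizumab shares.** Lowest category: odds 0.556/0.444 = 1.252; 1.252/2.63 = 0.476; 0.476/1.476 = 32.3%. The same step at each cut gives 32.3, 10.7, 19.3, 13.5, 24.3%.

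**Reproducing the planned size.** Whitehead's formula is N = 12(z₀.₉₇₅ + z₀.₉₀)² / [ln(OR)² (1 − Σp̄³)]. With ln 2.63 = 0.967 and Σp̄³ = 0.0976, N = 12 × 10.51 / (0.935 × 0.902) = 149.4, or 75 per group. At 76 per group, power is 90.5%. The plan's figure is reproduced.

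**Assumptions not in the documents.** Failures are 25, 50 or 100% of the lowest category. Values are spread evenly within the middle categories, the top category is set to 100%, and an observed non-decrease is 0%. Here a positive number is a fall in dose, so a failure value of −50 means 50% above baseline. At a 50% share, 1 − (1 − 0.278)(1 − 0.161) = 39% of pairs include an imputed value.

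**Expected-count data.** Counts are 24/8/15/10/19 for reslizumab and 43/8/11/6/8 for placebo. Hodges-Lehmann shift (95% limits), in percentage points:

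| Failure share | value −1 | −10 | −50 | −100 or lower | Wilcoxon p, every value |
|---|---|---|---|---|---|
| 25% | 14.5 (0.0, 38.7) | 15.8 (0.0, 38.9) | 23.6 (0.0, 50.0) | 23.6 (0.0, 53.1) | 0.0010 |
| 50% | 14.5 (0.5, 38.7) | 16.4 (0.5, 38.9) | 31.0 (0.5, 50.0) | 31.0 (0.5, 61.1) | 0.0011 |
| 100% | 14.5 (0.0, 38.7) | 16.7 (0.0, 41.7) | 19.8 (0.0, 61.1) | 19.8 (0.0, 66.7) | 0.0008 |

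**Simulated trials, 76 per arm, 500 per setting.** Going from −1 to −100, for shares of 25/50/100%:

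- Mean estimate: 12.5 to 21.5, 13.9 to 29.6, 13.2 to 20.0.
- Mean upper limit: 35.3 to 47.3, 36.9 to 59.0, 35.6 to 69.0.
- The estimate moved by more than 1 point in 66–97% of trials, and the upper limit in 98–100%.
- At the 100% share, 24% of trials had an upper limit above 100 points with a value of −100 or lower. There the limit keeps growing: its mean is 289 at −1000.

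A repeat simulation under the planned shares gave a mean estimate of about 12 at −1 and about 19–25 at −100, with mean upper limits of about 33–35 and 46–70. The size therefore varies between runs and assumptions; the direction does not.

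**Which values are admissible.** The observed minimum caps the failure value. Protocol 3.1.4.1 describes a post-exacerbation maintenance dose 2.5 mg above the pre-burst dose. If that happens before any taper, the rise is 2.5/10 = 25%, 2.5/7.5 = 33% or 2.5/5 = 50%. One such observed patient rules out −1. At a 50% share (300 trials, values uniform within categories), the mean estimate is 21.9 at −26, 23.9 at −34, 26.5 at −51 and 26.9 at −75 or lower. The mean upper limit goes from 39.9 at −26 to 56.5 at −100.

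**Strata.** Rank tests simulated on the five categories with two equal strata (assumed), OR 2.63:

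| Assumed stratum OR | Unstratified power | van Elteren power |
|---|---|---|
| 1 | 89.9% | 90.0% |
| 2 | 88.3% | 89.4% |
| 4 | 84.7% | 87.8% |

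Type I error of the unstratified test was 4.1–4.9%.

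**The case against.** The strongest reply is that nothing decisive rests on this. The analysis is a sensitivity check outside the testing hierarchy, its p-value does not depend on the failure value, and the lower limit stayed at 0.0–0.5 in the expected-count data. All of that stands.

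Next, a value of −1 is the extreme case. Once one observed patient's dose has risen by a quarter or more, the remaining movement in the estimate is about 5 points (21.9 to 26.9), and it is flat soon after −50. That also stands for the point estimate. It does not rescue the interval, whose upper limit still moves by 56.5 − 39.9 = 16.6 points.

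The failure share is not in the documents, so any single figure is conditional. That is why ranges are given. It is also fair to say that a percentage-point shift is easier to read than a probability, and that an unadjusted rank test is an acceptable supplementary choice.

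A reader might infer that stratification is needed because Table 3 makes the attainable percent reduction depend on the starting dose. The table does not support that. Starting doses of 5 to 30 mg all reach 0 mg. Doses of 35 and 40 mg end at 2.5 mg, which is 32.5/35 = 92.9% and 37.5/40 = 93.8%, still in the top category. What differs is the number of steps on the way.

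**Conclusion.** The point holds as a gap in specification. The worst-rank test is valid; the Hodges-Lehmann estimate and interval printed beside it are not determined by the SAP. Under the planned distributions, with an assumed failure share of 25–100% of the lowest category, the mean estimate runs from about 12 points (value −1) to about 19–25 (value −100). It is nearer 30 at a 50% share when the top category is set to 100%. The mean upper limit runs from about 33–35 to 46–70. The estimate mostly levels off below about −50, while the upper limit can keep moving.

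A reader might infer that the test is invalid, that its error rate is inflated, or that a trial conclusion would change. None of these follows: the p-value is the same for every value tried, and the unstratified test does not inflate type I error. Omitting the strata costs about 0–3 power points in the range assumed. The planned sample size is unaffected. The sign convention needs a line of text, because the intent is clear but the literal wording points the other way. This is a minor but worthwhile clarification.

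**What to change.** In SAP 6.3.2.2.3:

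1. Report a rank-based effect: the Mann-Whitney probability that a reslizumab patient does better than a placebo patient (ties counted as half), with its 95% CI. Add group medians on the worst-rank scale, printed as failure where the median falls among the failures.
2. If a percentage-point shift is also wanted, say that it is a between-group Hodges-Lehmann shift. Either state the failure value before unblinding or give the shift over a stated range of values.
3. State that failures rank worst, and in which direction, given the definitions in SAP 6.2.1 and 6.3.2.1.1.
4. Take the p-value from a van Elteren test stratified by OCS dose and age, with a rule for pooling sparse adolescent strata. Adolescents are excluded in several countries and the total is 152, so those cells may be very small.

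The cost is SAP wording and code, with no change to data collection or sample size. The downside is that the rank-based effect is not in percentage points, which item 2 covers if that scale is needed.

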2.3. Sample Size and Power Considerations

The primary efficacy variable and endpoint for this study is the percent reduction in the daily OCS dose during weeks 20 to 24 as compared with the dose at the end of the optimization phase. The study will be considered positive if the measure meets statistical significance at the respective predefined significance level. A statistically significant effect of reslizumab over placebo, as measured by the primary efficacy variable, is required to establish the efficacy of reslizumab treatment.

The sample size was calculated based on the following assumptions:

- Categorical reduction in OCS dose after 24 weeks of treatment will have the following distribution for the placebo group (based on [Bel et al 2014](#)):
 - 10.9% percent of subjects will have 90% to 100% reduction
 - 7.9% percent of subjects will have 75% to <90% reduction
 - 14.8% percent of subjects will have 50% to <75% reduction
 - 10.8% percent of subjects will have 0% to <50% reduction
 - 55.6% percent of subjects will have no reduction, loss of asthma control, or discontinuation from study drug
- The overall odds ratio between reslizumab and placebo based on proportional odds model will be 2.63
- Alpha level of 0.05

Based on the above assumptions, a sample size of 76 subjects per group will provide 90% power to detect a significant effect of reslizumab over placebo on the probability for a higher categorical reduction of OCS dose.

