4.3. Multiple Comparisons and Multiplicity

A fixed sequence multiple testing procedure will be implemented to test the primary and secondary variables while controlling the overall type I error rate at 0.05. If the resulting

two-sided p-value from the primary comparison is ≤ 0.05 , then the next comparison of interest (first secondary variable) will be interpreted inferentially at 0.05. This process continues through the secondary variables until either all comparisons of interest are interpreted inferentially, or until the point at which the resulting two-sided p-value for a comparison of interest is > 0.05 . At the point where $p > 0.05$, no further comparisons will be interpreted inferentially. The hierarchy of endpoints is as defined in Section 6.3.1.

No multiplicity adjustments will be made for other efficacy and exploratory analyses.

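### Total corticosteroid dose and exacerbation-steroid days are compared with no allowance for unequal follow-up, over a window that the SAP does not fix

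*SAP*

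**What the plan says.** SAP 6.3.2.2.3 (Other Sensitivity Analyses) adds two measures of corticosteroid burden. Cumulative dose is the sum of dose times duration, over oral, iv and im preparations in prednisone equivalents, taken over the whole study: "Analysis of the total cumulative dose of corticosteroids will be performed using an ANCOVA model with fixed effects for treatment". That model also adjusts for baseline OCS dose, OCS stratum and age stratum. For the second measure, "analysis of the total number of days corticosteroids taken for exacerbations will be performed using an ANOVA model" whose terms are the two strata and treatment. Neither model has follow-up time as divisor, covariate or offset.

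Other sections that bear on this:
- SAP 3.1 makes on-treatment data the main approach for all efficacy endpoints and cuts early discontinuers at last dose plus 4 weeks.
- SAP 4.4 reserves nonresponder handling for categorical OCS reduction, and multiple imputation for a sensitivity analysis of the primary variable. Everything else uses observed data only.
- SAP 5.2 counts patients entering the long-term extension (LTE) as study completers at week 24, and others at week 32.
- SAP 6.3.3.2 gives the exacerbation (CAE) rate model a log follow-up offset.
- Protocol 4.5.1 asks patients who stop study drug to keep attending to week 24. Protocol 4.5.2 treats all later data as missing after complete withdrawal.

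**The concern.** Both measures accumulate with time. If a patient stops being observed, the milligrams and steroid days that would have followed are left out of the sum, which is the same as scoring them zero. An arm that loses more follow-up then shows a lower burden for that reason alone.

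The plan deals with unequal follow-up in neighbouring analyses: the CAE rate has its offset, and the Wilcoxon analysis in the same SAP section ranks early withdrawals worst. SAP 5.2 also plans Kaplan-Meier plots to look for differential dropout. The burden totals have no such protection. In a steroid-sparing trial, total steroid exposure is a supportive result that is likely to be quoted.

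**Working it through.** **The plan's own figure.** The only computed figure is the primary sample size: "a sample size of 76 subjects per group will provide 90% power to detect a significant effect of reslizumab over placebo". The Whitehead formula is n per arm = 6(z_0.975 + z_0.90)² / [ln(OR)² (1 − Σp̄³)], where p̄ is the average of the two arms' category proportions. With OR 2.63 and the stated placebo distribution it gives 74.7, so 75 per arm, and power of 90.5% at 76. The figure reproduces, but it does not bear on this point; the plan states no figure for the burden analyses.

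**One patient, dose never reduced.** At 10 mg/day, 24 weeks gives 10 × 168 = 1680 mg and 12 weeks gives 10 × 84 = 840 mg, which is 50%.

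**One patient, tapering on schedule.** Table 3 (Protocol 3.1.4, SAP 2.1.4), after the 4-week induction, gives a 20 mg starter four-week levels of 20, 10, 7.5, 5, 2.5 and 0.
- 24-week total: 45 × 28 = 1260 mg.
- Total to week 12: 37.5 × 28 = 1050 mg, or 83%.
- Across the nine columns (40 mg down to 5 mg) the week-12 share is 84, 81, 89, 87, 83, 81, 90, 100 and 100%.

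**Arm-level bias, closed form.** Bias = dropout difference × dose missed per early leaver. Assume that leavers exit at week 12.
- Steady 12 mg/day (assumed): 0.05 × 84 × 12 = 50 mg; 0.15 × 84 × 12 = 151 mg.
- Table 3 from 20 mg: 0.05 × (1260 − 1050) = 10.5 mg; 0.15 × 210 = 31.5 mg.

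**Simulated trials with no drug effect.** 4,000 trials, 76 per arm. Assumptions, none from the documents: exits spread evenly over weeks 4 to 20; baseline doses of 5 to 40 mg, mostly 5 to 20; mean dose after week 4 at 70% of baseline (SD 30 points) with no further taper; overdispersed CAE rate of 1.5 per year; 9 steroid days per CAE. The age stratum was omitted.

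| Dropout, placebo v reslizumab | Raw total: false difference (rejection) | Total / days observed: rejection | Steroid days: false difference (rejection) |
|---|---|---|---|
| 10% v 10% | +4 mg (4.5%) | 5.0% | -0.02 (5.0%) |
| 10% v 20% | -81 mg (9.8%) | 5.0% | -0.27 (4.8%) |
| 10% v 30% | -164 mg (26.8%) | 6.5% | -0.63 (7.8%) |
| 20% v 10% | +84 mg (11.3%) | 5.2% | +0.27 (5.4%) |

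With the Table 3 taper built in, at 10% v 20% dropout, the raw total was off by about -49 to -69 mg (rejection 8% to 11%). Mean daily dose was off by about +24 to +38 mg-equivalent, in the opposite direction (6% to 7%).

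**Why dividing by days observed over-corrects.** The 20 mg taperer averages 1050 / 84 = 12.5 mg/day if last seen at week 12, against 1260 / 168 = 7.5 mg/day if completing. A 5-point imbalance shifts the arm mean by 0.05 × 5 × 168 = 42 mg-equivalent the other way, against 10.5 mg for the raw total.

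**The window.** Read literally, the whole study ends at week 24 for LTE entrants and week 32 for others. At 10 mg/day that is 1680 v 2240 mg, 25% lower for the same daily dose. Protocol 5.3 records medication from screening, so variable pre-randomization time could count as well. Under SAP 3.1, by contrast, the sum stops at last dose plus 4 weeks for discontinuers, even those followed to week 24.

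**The case against.** The strongest case against runs as follows. Patients who stop study drug are asked to stay to week 24 on study prednisone, so under a literal whole-study reading only complete withdrawals are cut short. OCS dose is already analysed as period means by MMRM (SAP 6.3.2.2.1). Differential dropout will be plotted. The burden analyses are sensitivity analyses outside the fixed sequence.

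Most of this stands as a limit on importance. It does not remove the defect: complete withdrawals remain, the on-treatment default would truncate discontinuers whose later data were collected, and the MMRM does not cover iv and im steroids.

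A reader might infer three stronger things that the documents do not support:
- That early dropout will make reslizumab look steroid-sparing. The direction depends on which arm loses more follow-up, and the documents give no dropout rate for either.
- That someone leaving at week 12 contributes half a completer's milligrams. That holds only if the dose never falls; on the Table 3 schedule the share is 81% to 100%.
- That dividing by days observed settles the matter. It suits steady doses only, and reverses the bias when early leavers are seen mainly in the untapered weeks.

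**Conclusion.** The point holds as a defect in two supportive analyses. Unobserved time is scored as zero burden, and the window is not fixed. Bias arises only when follow-up differs between arms, and it favours the arm that loses more.

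Its size rests on assumed dropout and on how many patients taper. The 50 to 151 mg figures apply to a steady 12 mg/day, with dropout differences of 5 and 15 points and exit at week 12. For a 20 mg starter tapering on schedule the same differences give 10.5 to 31.5 mg. The effect on exacerbation-steroid days is small: under the simulation assumptions, rejection stays near 5% with a 10-point imbalance and reaches 7.8% with a 20-point one.

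Nothing here touches the primary analysis or type I error control, since SAP 4.3 and 6.3.1 leave both measures outside the testing sequence.

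**What to change.** Amend SAP 6.3.2.2.3 before unblinding:
1. Use one window for both measures: first dose to week 24, including data collected after study drug is discontinued. State that this overrides the on-treatment default in SAP 3.1.
2. Analyse exacerbation-steroid days with a negative binomial model and a log(days observed) offset, in line with the CAE model.
3. For patients who leave before week 24, multiply impute the period-level prednisone-equivalent dose for the unobserved periods before summing. This extends Appendix A, which currently covers OCS dose only, to iv and im steroids.
4. Report mean daily dose (total / days observed) as a companion analysis, with a note that it over-corrects for patients who leave before tapering. Keep raw totals descriptive.

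The cost is SAP wording and some extra programming, mainly for the imputation. No new data are needed.
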